6.7.2. Virology and Resistance Monitoring

To assess the potential for emergence of resistance to presatovir, population sequencing of the RSV F gene will be conducted on evaluable nasal swab samples collected from presatovir and placebo-treated RSV-infected subjects according to the Virology Analysis Plan. PPD

Population sequencing of the RSV F gene will be conducted on evaluable nasal swab samples from all presatovir-treated RSV-infected subjects in this group. Any mutation in the F gene identified by population sequencing in presatovir-treated subjects relative to the pretreatment baseline sequence will be characterized phenotypically following their introduction into wild-type RSV using an established reverse genetics system. The susceptibility of the F mutant recombinants to presatovir will be assessed in cell-based antiviral susceptibility assays to determine whether each treatment-emergent mutation (TEM) confers reduced susceptibility to the compound.

6.7.3. FLU-PRO Questionnaire

The FLU-PRO will be self-administered after informed consent and prior to all other study procedures. The FLU-PRO is currently being validated for the evaluation of symptoms in patients who are infected with influenza. Due to the lack of validated tools for the evaluation of RSV symptoms, and significant overlap between RSV symptoms and influenza symptoms, this tool will be used to assess change in RSV symptoms in this study. This questionnaire will be completed by subjects on Days 1/Baseline, 3, 5, 7, 9, 14, 21 and 28/End of Study.

6.7.4. Vital Signs

This assessment will include body temperature, heart rate, respiratory rate, and blood pressure. The subject is required to sit quietly for approximately 2 minutes prior to obtaining VS. Vital signs will be collected at Screening and on Days 1/Baseline, 7, 14, 21, and 28/End of Study.

6.7.5. Oxygen Requirement Assessment

The requirement for oxygen will be assessed according to whether the subject requires any supplemental oxygen (yes or no) on Day 1/Baseline and a new home oxygen prescription (yes or no) on Days 3, 5, 7, 9, 14, 21, and 28/End of Study.

6.7.5.1. Oxygen Saturation Assessment

Oxygen saturation assessment will begin by first asking the subject to sit quietly for 1 minute. Oxygen saturation will be recorded while breathing room air. If the subject is prescribed supplemental O₂ for chronic use prior to this current illness (eg, 2L/min via nasal cannula), the prescribed amount should be noted in the eCRF and should be used during the O₂ saturation assessment. Any additional supplemental O₂ being used (ie, above room air or prescribed amount for chronic use prior to this current illness) should be removed for a period of 30 seconds prior to this assessment. The O₂ saturation will be documented in the source at regular intervals during the 2-minute testing period. Oxygen saturation evaluation will be considered complete when the 2-minute period has elapsed, or when the subject achieves a saturation of $\leq 88\%$, whichever is achieved first. The lowest O₂ saturation recorded over the 2-minute interval will be captured in the eCRF. If the subject is unable to tolerate removal of supplemental oxygen for this assessment (eg, subject dependent on high dose oxygen or on mechanical ventilation), notation that the oxygen saturation could not be assessed by this protocol should be noted with the reason recorded.

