8.3. Data Handling Conventions

Missing data can have an impact upon the interpretation of the trial data. As this study is of short duration, it is anticipated that missing data will be minimal. In general, values for missing data will not be imputed. For laboratory data, a missing Baseline value will be replaced with a screening value, if available; otherwise it will be treated as normal (ie, Grade 0; no toxicity grade) for the summary of graded laboratory abnormalities. A retest value may be used if the first test is invalidated.

Values will not be imputed for missing vital sign and other safety data; however, a missing Baseline value will be replaced with a Screening value, if available.

Details for the handling of missing data due to subject discontinuation or other reasons, including unusable and spurious data, and rules for determining major and minor protocol deviations will be described in the SAP.

All available data for subjects that do not complete the study will be included in the data listings.

Tables that include both individual subject PK data and summary statistics will present all available data, but only subjects in the PK analysis will be included in the summary statistics.

Viral load data will be log transformed prior to analyses.

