### **3.6. Missing Data and Outliers**

#### **3.6.1. Missing Data**

In general, missing data will not be imputed unless methods for handling missing data are specified. Exceptions are presented in this document.

For missing last dosing date of study drug, imputation rules are described in Section 4.2.1. The handling of missing or incomplete dates for AE onset is described in Section 7.1.5.2, and for prior and concomitant medications in Section 7.4. The handling of missing data in analyses of the efficacy endpoints is discussed in Section 6.

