15.11.6.2.2	Chemistry Test: ALT (U/L) and Change from Baseline	Safety Analysis Set
15.11.6.2.3	Chemistry Test: Alkaline Phosphatase (U/L) and Change from Baseline	Safety Analysis Set
15.11.6.2.4	Chemistry Test: Total Bilirubin (mg/dL) and Change from Baseline	Safety Analysis Set
15.11.6.2.5	Chemistry Test: Blood Urea Nitrogen (mg/dL) and Change from Baseline	Safety Analysis Set
15.11.6.2.6	Chemistry Test: Creatinine (mg/dL) and Change from Baseline	Safety Analysis Set
15.11.6.2.7	Chemistry Test: Creatinine Clearance (mL/min) and Change from Baseline	Safety Analysis Set
15.11.6.4.1.1	Treatment Emergent Laboratory Abnormalities	Safety Analysis Set
15.11.6.4.1.2	Treatment Emergent Laboratory Abnormalities by Age Group (<65 Years or $\geq 65$ Years)	Safety Analysis Set
15.11.6.4.1.3	Treatment Emergent Laboratory Abnormalities by Sex (Male or Female)	Safety Analysis Set
15.11.6.4.2	Treatment Emergent Grade 3 or Above Laboratory Abnormalities	Safety Analysis Set
15.11.6.4.3	Treatment Emergent Marked Laboratory Abnormalities	Safety Analysis Set
15.11.6.5	Liver-Related Laboratory Abnormalities	Safety Analysis Set
15.11.6.6	Shift in Troponin Results	Safety Analysis Set
15.11.7.1.1	Vital Signs: Diastolic Blood Pressure (mmHg) and Change from Baseline	Safety Analysis Set
15.11.7.1.2	Vital Signs: Systolic Blood Pressure (mmHg) and Change from Baseline	Safety Analysis Set
15.11.7.1.3	Vital Signs: Pulse Rate (beats per minute) and Change from Baseline	Safety Analysis Set
15.11.7.1.4	Vital Signs: Respiration Rate (breaths per minute) and Change from Baseline	Safety Analysis Set

Table Number	Title	Analysis Set
15.11.7.1.5	Vital Signs: Temperature (Celsius) and Change from Baseline	Safety Analysis Set
15.11.7.1.6	Vital Signs: O 2 Saturation (%) and Change from Baseline	Safety Analysis Set
15.11.7.3.1	Prior Medication by Drug Class and Preferred Drug Name	Safety Analysis Set
15.11.7.3.2	Concomitant Medication by Drug Class and Preferred Drug Name	Safety Analysis Set
15.11.7.3.3	Prior Ribavirin, Palivizumab, and IVIG by Drug Class and Preferred Drug Name	Safety Analysis Set
15.11.7.3.4	Concomitant Ribavirin, Palivizumab, and IVIG by Drug Class and Preferred Drug Name	Safety Analysis Set
15.11.9.1	Shift in Electrocardiogram Assessment Results	Safety Analysis Set
15.11.9.2	Subjects with New Abnormalities ECG at Post-baseline	Safety Analysis Set

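### Oxygen saturation is summarised only as observed continuous values, although the test leaves out subjects who cannot come off added oxygen, and the vital-sign threshold summary promised in the protocol is missing from the SAP

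*Protocol*

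**What the plan says.** **The test (Protocol 6.7.5.1).** The subject breathes room air, or the oxygen prescribed for chronic use before this illness. Any further oxygen is removed for 30 seconds beforehand. The test normally runs for two minutes, but a low reading can end it sooner: "or when the subject achieves a saturation of $\leq 88\%$, whichever is achieved first". What goes into the database is set out in a separate sentence: "The lowest O₂ saturation recorded over the 2-minute interval will be captured in the eCRF". A subject who cannot tolerate removal of oxygen, with high-dose oxygen and mechanical ventilation as the examples, has no value; instead, "notation that the oxygen saturation could not be assessed by this protocol should be noted with the reason recorded".

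**Missing data.** Protocol 8.3: "Values will not be imputed for missing vital sign and other safety data", except that a missing Baseline value may be replaced by a Screening value. SAP 3.6.1: "In general, missing data will not be imputed unless methods for handling missing data are specified". No method is specified for saturation.

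**Reporting.** SAP 13.1 lists saturation among the vital signs as Table 15.11.7.1.6, ending "Saturation (%) and Change from Baseline", on the Safety Analysis Set. Figure 15.11.7.1.6 shows median and quartiles by visit, and Listing 16.2.8.2 gives the by-subject data. SAP 7.3 sets the vital-sign content (baseline, value at each visit, change) without naming saturation. SAP 3 sets the statistics for continuous variables: n, mean, SD or SE, median, quartiles, minimum and maximum.

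**Threshold commitment.** Protocol 8.7.3 says that vital signs will also be summarised against pre-determined clinically relevant thresholds. Neither SAP 7.3 nor the SAP table list has such a summary. SAP 7.7, the section for departures from the protocol's safety analyses, mentions only the cancelled DMC meeting.

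**The concern.** A saturation value is absent for the very reason that makes it informative: the subject depends on added oxygen or a ventilator. A summary of the remaining values describes the healthier part of each arm at that visit. If one arm deteriorates more, it loses more of its worst subjects from the mean, the median and the quartiles, and the arms look more alike than they are. This can hide harm or benefit.

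The early stop adds a second, smaller loss. Once a reading of 88% or lower is seen the test may end, so any deeper fall later in the two minutes is not observed.

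A threshold count with a not-assessable category would avoid both problems. Protocol 8.7.3 already commits the trial to threshold summaries for vital signs, so their undeclared absence from the SAP is also an inconsistency between the two documents.

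**Working it through.** The documents state no power, expected rate or effect size for saturation, so there is no plan figure to reproduce. The check has three parts.

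**1. What the early stop loses.** Assume a reading every 10 seconds and a linear fall.

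| Start | Fall per reading | Value recorded | Two-minute nadir |
|---|---|---|---|
| 94% | 1 point | 88% | 82% |
| 90% | 1 point | 88% | 78% |
| 86% | 1 point | 86% | 74% |
| 80% | none | 80% | 80% |

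A later, deeper nadir is lost, but a first reading well below 88% is kept as measured. The stop does not change whether a subject counts as at or below 88%.

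**2. What missing values alone do to the difference in means.** All inputs are assumptions:
- non-severe subjects: mean 95%, SD 2
- severe subjects: mean 82%, SD 4, the value they would show if tested
- severe share p: 15% in one arm, 5% in the other
- fraction m of severe subjects who are unassessable: the same in both arms
- every assessable value recorded as it is, with no loss from the early stop

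The mean shortfall below 95 among assessable subjects is 13 × p(1 − m) / (1 − pm), where 13 = 95 − 82.

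| m | Shortfall, p = 0.15 | Shortfall, p = 0.05 | Difference | Lost |
|---|---|---|---|---|
| 0 | 13 × 0.15 = 1.95 | 13 × 0.05 = 0.65 | 1.30 | 0% |
| 0.25 | 13 × 0.1125/0.9625 = 1.52 | 13 × 0.0375/0.9875 = 0.49 | 1.03 | 21% |
| 0.50 | 13 × 0.075/0.925 = 1.05 | 13 × 0.025/0.975 = 0.33 | 0.72 | 45% |
| 0.75 | 13 × 0.0375/0.8875 = 0.55 | 13 × 0.0125/0.9625 = 0.17 | 0.38 | 71% |

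The order statistics shrink too. At m = 0.50, from the quantiles of the same mixtures, the difference in medians is 0.16 against 0.31 with no missing values, and the difference in first quartiles is 0.32 against 0.76.

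If both arms have the same p and m, the difference between arms is unbiased at zero, but the level is not: with p = 0.15 and m = 0.50 each arm shows a shortfall of 1.05 instead of 1.95.

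**3. What a count would show on the same inputs.** With everyone assessable, the share at or below 88% is 0.15 × Φ(1.5) + 0.85 × Φ(−3.5) = 14.0% in one arm and 0.05 × Φ(1.5) + 0.95 × Φ(−3.5) = 4.7% in the other. At m = 0.50 the table would show 7.0% at or below 88% and 7.5% not assessable, against 2.4% and 2.5%. The contrast stays visible whatever m is, because unassessable subjects move to their own row instead of leaving the table.

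**The case against.** Four arguments for leaving the plan alone deserve weight.

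*The planned output is richer than a mean change.* This stands. It includes n, values by visit, median, quartiles, minimum, maximum and a listing. The n shows how many values are missing at a visit, but not why. The minimum shows one subject per arm. The listing gives no comparison between arms. As shown above, medians and quartiles shrink as well.

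*The worst subjects are counted elsewhere.* This stands in part. Table 15.9.3.10 covers ventilation, 15.9.3.12 covers new home oxygen, 15.9.3.8 to 15.9.3.11 cover hospital, ICU and ventilator days, and respiratory adverse events are tabulated on the Safety Analysis Set. But those efficacy tables use the FAS, which drops subjects whose baseline viral load is below the LLOQ, and they run through Day 28, not by visit. As titled, neither the ventilation nor the home-oxygen table counts an inpatient on high-dose oxygen who is not ventilated and has no new home prescription. That subject may be unassessable under 6.7.5.1.

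*The stakes are low.* This stands. In the visible plan saturation is a descriptive safety measure with no formal test, and is neither a primary nor a secondary endpoint.

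*The protocol does not itself call saturation a vital sign.* Protocol 6.7.4 lists only temperature, heart rate, respiratory rate and blood pressure. The threshold commitment reaches saturation because the SAP's own table list files it there.

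A reader might go further and infer that values are clipped at 88%, so that a subject at 80% is entered as 87% or 88%. The documents set no floor; that holds only for a gradual fall during the test. A reader might also infer that the unassessable subjects vanish without trace. They do not, since the reason must be noted.

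**Conclusion.** The point holds as a modest defect in a safety display. Two things can be read directly from the documents: subjects who cannot come off added oxygen have no value and no category in the SAP, and the vital-sign threshold summaries in Protocol 8.7.3 are absent from the SAP without being declared in SAP 7.7. It follows that the observed-value summaries understate desaturation to the extent that severity makes subjects unassessable.

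The size is illustrative. On the assumed rates, missing values alone remove 21% to 71% of a 1.30-point difference as the unassessable fraction of severe subjects goes from 25% to 75%, and none if all are assessable. The 'true' difference assigns a saturation off added oxygen to subjects for whom the protocol says it could not be assessed, so it is a benchmark for the display, not an estimable quantity. The early stop adds a further loss only for subjects whose saturation would have kept falling. No primary or secondary conclusion is affected.

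**What to change.** In SAP 7.3 and the table list, add one table on the Safety Analysis Set giving, by visit and arm, the number (%) of subjects:
- (a) above 88%
- (b) at or below 88%
- (c) not assessable because supplemental oxygen or ventilation could not be removed

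Use the recorded value and the recorded reason. The 88% cut-off is already in Protocol 6.7.5.1. Keep Table and Figure 15.11.7.1.6 as planned, labelled 'assessable subjects'. Whether (b) and (c) are also pooled is a matter of preference. For the other vital signs, either supply the threshold summaries promised in Protocol 8.7.3 or declare in SAP 7.7 that they are dropped.

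Confirm that the reason for non-assessment is in the clinical database. Protocol 6.7.5.1 names the eCRF for the prescribed oxygen amount and for the lowest value, but does not say where the reason is held.

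The test procedure does not change. Two sentences in 6.7.5.1 should be reconciled: the one asking for the lowest value over the two-minute interval, and the one allowing the test to finish before that interval has run.

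The cost is one extra descriptive table and, if the reason was not entered in the database, its retrieval from source. No new assessment is needed.

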6.7.6. Safety Labs

When available, the most recent laboratory values (obtained ≤ 7 days prior to Screening) may be used for eligibility assessment, with the exception of RSV results and pregnancy testing. If an existing laboratory value is not available for eligibility assessment, the test will be performed using the local hospital laboratory. All testing of samples obtained after the Screening assessments (with the exception of an additional local troponin test on Day 1/Baseline and Day 28/End of Study) will be performed at a central laboratory selected by GSI.

Central laboratory testing of blood specimens for safety analysis will include CBC, sodium, potassium, chloride, CO₂, BUN, creatinine, glucose, AST and ALT, alkaline phosphatase, total bilirubin and CK on Days 1/Baseline, 7, and 14 (pre-dose) and on Days 21 and 28/End of Study.

Local laboratory testing of troponin will also be done at Day 1/Baseline and Day 28/End of Study for timely safety evaluation by the investigator. Local troponin testing will be done in accordance with the standard assay available at the site.

If the subject is seen at the site for any reason (eg, hospitalization, clinic, or site visit) between Days 2 to 14, a blood draw for troponin measurement is required. If the subject is at the site on more than 1 occasion between this timeframe, only 1 protocol-mandated measurement is required, but it should be obtained at the earliest feasible time and during the same study visit as the ECG measurement described below.

Samples will be sent to the local lab at the clinical site for troponin analysis using the laboratory-based assay specific to the local trial site (eg, troponin I or T). Point-of-care “rapid” troponin tests are not acceptable for protocol-mandated troponin testing. The baseline troponin test must be pre-dose. Troponin testing done for the purposes of patient care on the same day as a protocol-required test day may be used, provided the test is completed at the protocol-directed time and is a laboratory-based assay. Troponin results should be verified before the subject leaves the clinical site in case a troponin value is positive and further medical care is advised. Any additional troponin measures obtained for the purposes of patient care also require collection.

Any test showing an increase of serum AST or ALT $> 3 \times$ ULN or TB $> 2 \times$ ULN, will be repeated within 48 to 72 hours for ALT, AST, ALP, and TB. If the repeat values are unchanged or are normalizing, monitoring will continue at weekly intervals until the results are acceptable or normalized. If any value has increased further from normal, immediate close observation is required. If close monitoring is not possible, IMP administration will be discontinued.

Local urine or serum pregnancy tests will occur for all females of childbearing potential at Screening, within 1 day prior to IMP administration, and on Days 7 and 14.

